# 8.3.5 Severity of Adverse Event or Suspected Adverse Drug Reaction

Adverse events and suspected ADRs (ie, potentially drug related AEs) will be classified depending on their severity according to the following definitions:

Mild: an AE which is well tolerated by the subject, causing minimum degree of malaise and without affecting normal activities.

**Moderate**: an AE that interferes with the subject's normal activities.

**Severe**: an AE that prevents the subject from performing their normal activities. This category is further subdivided into Grade 3-5 AEs defined according to CTCAE criteria, US Department of Health and Human Services, NIH, and NCI.

Adverse events and suspected ADR severity gradation must be distinguished from AE and suspected ADR seriousness gradation, which is defined according to event consequence. For example, headache can be mild, moderate or severe but not necessarily serious in all these cases.

The investigator will be responsible for assessing the AE and suspected ADR intensity during the clinical trial, taking into account current criteria included in this section.

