## 7.2.5 Day 7 Healthcare Provider Visit

Assessments include the following:

- Ordinal Scale assessment
- NEWS (Appendix 2)
- Surveillance for COVID-19 symptoms (detailed checklist) including: fever, cough, shortness of breath, fatigue, myalgia etc.

PIEDIC	Number	BIG-CL-PRT-000028	Version 5.0	2.0	Status	Effective	Effective Date 13	13-Oct-2021	
JINICOLO	GC2010 - A	Multicenter, Randomized, Double-blind, Pa	Parallel Gro	Parallel Group Study to Evaluate the	valuate the Safet	ety and Efficacy of	00	24 -6 406	
Contraction of the contraction o	Anti-COVID-	D-19 Immune Globulin (Human) 20% (C19-IG 20%) versus Placebo in As	9-IG 20%) ve	rsus Placebo	in Asymptoma	tic Ambulatory	Lage	901 10 17	

- Vital signs (temperature, systolic and diastolic blood pressure, pulse, respiratory rate)
- Record oxygen saturation (specify on or off oxygen supplementation)
- Record any Medically Attended Visit(s) for management/treatment of COVID-19 (other than routine study-directed visits) in any setting, specifying type (eg, Emergency department, urgent care, outpatient clinic/professional setting for direct inperson/telemedicine medical assessment and care of COVID-19 provided by licensed healthcare personnel)
- Overall assessment of COVID-19 symptom severity graded as follows:

No symptoms: No COVID-19 symptoms present.

Mild: Mild symptoms causing no or minimal interference with ability to perform usual activities with intervention not indicated (note: limitations due to quarantine do not count towards grading assignment)

Moderate: Moderate symptoms causing greater than minimal interference with usual functional activities with intervention indicated (note: limitations due to quarantine do not count towards grading assignment)

Severe: Severe symptoms causing inability to perform usual functional activities with intervention or hospitalization indicated.

Potentially Life-threatening: Potentially life-threatening symptoms causing inability to perform basic self-care functions with intervention indicated to prevent permanent impairment, persistent disability, or death

- If subject requires supplemental oxygen post randomization: Record any supplemental oxygen administration (type, %, flow start/end date/time)
- If subject requires hospital admission post randomization: Record hospital admission and discharge dates
- If subject requires ICU admission post randomization: Record ICU admission and discharge dates

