# 8 ASSESSMENT OF SAFETY

# 8.1 Safety Parameters

The safety and tolerability of C19-IG 20% in subjects with COVID-19 will be evaluated in this study. Safety variables will include:

- Cumulative incidence of treatment-emergent SAEs and potentially related SAEs through Day 60 Phone Check
- Cumulative incidence of Grade 3-5 TEAEs and potentially related severe TEAEs through Day 29 as defined in the CTCAE, US Department of Health and Human Services, NIH, and NCI through Day 29
- Cumulative incidence of all TEAEs and potentially related TEAEs through Day 29
- Change from baseline in key biochemical parameters of organ function/dysfunction: ALT;
   LDH; absolute lymphocyte count; creatinine through Day 14

In this clinical study, disease progression is defined as the worsening of a subject's condition attributable to the disease for which the investigational product is being studied. It may be an increase in the severity of the targeted disease and/or increases in the symptoms of the targeted disease. Anticipated symptoms of COVID-19 include fever, cough, hypoxia, dyspnea, hemoptysis, myalgia, fatigue, pharyngitis which may develop at any time during the course of the disease. The development of COVID-19 symptoms during the clinical study

Number BIG-CL-F	BIG-CL-PRT-000028	Version 5.0		Status	Effective	Effective Date 13-Oct-2021	13-Oct-2021	
GC2010 - A Multicente	ter, Randomized, Double-t	Parallel Gro	up Study to E	olind, Parallel Group Study to Evaluate the Safety ar	ety and Efficacy of	~ ~ d	901 3- 22	
Anti-COVID-19 Immi	19 Immine Glohilin (Himan) 20% (C19-IG 20%) versiis Placebo in Asvmptomati	3-IG 20%) ve	Placeho	in Asymptoma	atic Ambulatory	Lage	001 10 //	

should not be recorded as individual TEAEs, unless there is evidence suggesting a causal relationship between C19-IG 20%/placebo and the TEAE.

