# 8.3.8 Adverse Event Documentation

All AEs and SAEs occurring on Day 1 through the Day 29 (±1 day)/Final Visit must be fully recorded in the subject's medical record and CRF, and SAE report form (if serious).

At the time of the Day 60 (±2 days) Phone Check any additional SAEs/non-serious AEs will also be collected and recorded.

It is the responsibility of the investigator to ensure that AEs are appropriately recorded.

AEs will be collected through directly observed events or spontaneously volunteered by the subject. Clearly related signs, symptoms and abnormal diagnostic procedures should preferably be grouped together and recorded as a single diagnosis or syndrome wherever possible.

The following variables must be recorded:

- The verbatim term (a diagnosis is preferred)
- Date/time of onset
- Date/time of resolution
- Severity (mild, moderate, severe [Grade 3 to Grade 5])
- Causality (unrelated, possibly related, definitely related)\*
- Seriousness (yes, no)
- Action taken (with regard to IP)
- Other action (to treat the event)
- Outcome and sequel (follow-up on AE)

\*Causality assessment will be made only when the AE occurs after the subject has initiated at least one infusion of the IP. An AE occurring before subject's exposure to IP will be always labeled as "unrelated".

For AEs that occur during infusions, the infusion rate in effect at the time of onset of the AE, the time of onset of the AE and the time of AE change materially in intensity and/or resolve will be captured.

In addition to the investigator's own description of the AE, each AE will be encoded according to the Medical Dictionary for Regulatory Activities (MedDRA).

For example, a laboratory test abnormality considered clinically significant, eg, causing the subject to withdraw from the study, requiring treatment or causing apparent clinical manifestations, or judged clinically significant in the context of the subject's medical history by the investigator, should be reported as an AE.

Each event must be described in detail along with start and stop dates, severity, relationship to IP, action taken and outcome. Each event must be adequately supported by documentation as it appears in the subject's medical or case file.

[figure not shown]

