In the remaining summary tables, the incidence of TEAEs will be calculated by dividing the number of subjects who have experienced the event by the total number of subjects. Thus, the incidence of TEAEs is shown in terms of the total number of subjects and not in terms of the total number of episodes. If a subject has repeated episodes of a particular TEAE, only the most severe episode, or the episode with the strongest causal relationship to IP, will be counted in the summary tables.

A subject with more than one type of TEAE in a particular SOC or PT will be counted only once in the total of subjects experiencing TEAEs in that particular SOC or PT.

All occurrences of all AEs and SAEs will be listed for each subject, grouped by treatment group. The listing will contain the following information: treatment group, verbatim term, SOC, PT, severity and grade (mild [Grade 1], moderate [Grade 2], severe [Grade 3], Life-threatening [Grade 4], Fatal [Grade 5]), relationship to IP, date/time and day of onset, date/time and day of resolution, action taken with regard to IP, whether additional non-drug or drug treatment was given to treat the adverse event, the outcome, whether the event was an SAE, whether it led to study withdrawal, whether it occurred during IP infusion, and whether it is a TEAE. Listings will be sorted by treatment group, subject identification number, onset date, SOC, and PT. If the onset date is completely missing, then these events will be presented first. If the onset date is missing a month or a day, then these events will be presented before any complete dates.

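### Grade 3-5 TEAEs are defined directly by CTCAE in the safety endpoint but through an activity-based 'severe' category in the AE severity rule, and the two are not reconciled

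*Protocol*

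**What the plan says.** **Endpoint.** Protocol 8.1 lists "Cumulative incidence of Grade 3-5 TEAEs and potentially related severe TEAEs through Day 29 as defined in the CTCAE" among the safety variables; Protocol 4.1.4 and SAP 2.2.4 carry the same endpoint. Footnote d of the visit schedule (Protocol Appendix 1, SAP Appendix A) is attached to the row for recording SAEs and TEAEs. It also says that Grade 3-5 events are defined by CTCAE. None of these places mentions normal activities, and none names a CTCAE version.

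**Severity rule.** Protocol 8.3.5 classifies AEs by their effect on the subject's activities. A mild AE is well tolerated, "causing minimum degree of malaise and without affecting normal activities"; a moderate one interferes with them; a severe one is "an AE that prevents the subject from performing their normal activities". CTCAE enters at that point only: "This category is further subdivided into Grade 3-5 AEs defined according to CTCAE criteria". The investigator is to assess intensity "taking into account current criteria included in this section".

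**Recording.** The severity field in Protocol 8.3.8 offers the same three words and attaches Grades 3 to 5 to severe alone.

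**SAP.** Section 7.2.2 defers to Protocol 8.2.5 for severity, but Protocol 8.2 has no subsections and the severity text is in 8.3.5. The AE listing in SAP 7.2.5 shows severity and grade together as "mild [Grade 1], moderate [Grade 2], severe [Grade 3], Life-threatening [Grade 4], Fatal [Grade 5". The same section has tables by greatest severity (i.3 and v) and by Grade ≥3 (i.4, vi and vii).

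**The concern.** An endpoint defined by CTCAE needs a CTCAE grade for every AE that might qualify. Protocol 8.3.5 supplies one only after the AE has been judged to prevent normal activities. That is a different question from whether it meets a CTCAE criterion, so the two can disagree for the same event.

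What is at stake is the numerator of a named safety endpoint, for a product with which Protocol 2.2 reports no clinical experience to date. Sites that follow 8.3.5 and sites that follow footnote d could grade the same event differently, and readers of the Grade ≥3 tables could not tell which rule produced them.

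**Working it through.** No arithmetic applies, because the documents give no AE rates. The check is to set the rules side by side and follow one event through each.

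| Place | What makes an AE Grade 3-5 | Activity test? |
|---|---|---|
| Protocol 4.1.4 and 8.1; SAP 2.2.4 | CTCAE | No |
| Footnote d, Protocol Appendix 1 and SAP Appendix A | CTCAE | No |
| Protocol 8.3.5 | CTCAE, within severe only | Yes: must prevent normal activities |
| Protocol 8.3.8 recording field | Being recorded as severe | Yes, through 8.3.5 |
| SAP 7.2.5 listing | Grade paired with the severity word | Yes, if the word comes from 8.3.5 |

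**Step 1: an event on which the rules can differ.** Take an AE that meets a CTCAE Grade 3 criterion but does not prevent normal activities. A possible case is a laboratory finding. Protocol 8.3.8 makes "a laboratory test abnormality considered clinically significant" reportable as an AE, and one of its grounds is the investigator's judgment in the light of medical history, which requires no symptoms. That CTCAE would grade such a finding 3 or higher is an assumption, since neither document reproduces its criteria.

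**Step 2: endpoint and footnote d.** The event meets CTCAE Grade 3, so it is counted.

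**Step 3: Protocol 8.3.5 taken literally.** The event does not prevent normal activities, so it is not severe. It is mild or moderate, and the field in 8.3.8 carries no grade for either. With the SAP 7.2.5 pairing it becomes Grade 1 or Grade 2, and it is absent from tables i.4, vi and vii.

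**Step 4: does the SAP settle it?** No. Its severity section points to a protocol section that does not exist. It tabulates severity and grade separately but gives no rule for assigning a grade independently of the severity word.

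**Step 5: a second mismatch.** In Protocol 8.3.5 and 8.3.8, severe spans Grades 3, 4 and 5. In SAP 7.2.5 it is Grade 3 only, with life-threatening and fatal as further levels. The tables by greatest severity therefore use either a three-level or a five-level scale, depending on which document is followed.

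**Result.** One endpoint has two possible numerators. They coincide only if every AE that is Grade 3 or higher by CTCAE also prevents normal activities.

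**The case against.** The strongest reply is that the endpoint and footnote d are clear, and that footnote d is itself a recording instruction, so a well-trained site would grade by CTCAE. The SAP line that pairs words with grades describes the content of a listing and is not stated as a derivation rule for the tables. Separate severity and Grade ≥3 tables are what one would expect if every AE had its own grade. The CRF and its completion guide are not among the documents and may ask for a grade directly.

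Much of this stands, and it rules out several stronger readings.

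- A reader might infer that CTCAE can be reached only through severe, so that the endpoint certainly loses events. That is true of 8.3.5 and 8.3.8 taken alone. The endpoint and footnote d apply CTCAE directly, so the supportable statement is that events may be lost if 8.3.5 is applied literally.
- A reader might infer that changes in organ function would go unseen. They would not. Change from baseline in ALT, LDH, lymphocyte count and creatinine is its own safety endpoint, and SAP 7.3 adds raw values, shift tables on high/low flags and out-of-range flags. Important medical events can also qualify as SAEs under Protocol 8.3.7 whatever their severity class. What these outputs do not give is a count of subjects with Grade ≥3 events.
- A reader might infer that under-grading adds noise and hides a difference between arms. SAP 7 plans no formal testing of safety, and nothing in the documents supports a claim about lost sensitivity.
- A reader might infer that home confinement distorts the activity test, since COVID-19 symptom severity is graded with the note that "limitations due to quarantine do not count towards grading assignment" and AEs are not. Protocol 8.3.5 asks what the AE itself does to activities, so the missing note is a matter of clarity and the point does not rest on it.

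What the reply does not do is reconcile the two rules. The investigator is told to use the criteria of 8.3.5, and no section gives footnote d precedence.

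**Conclusion.** The point holds as an unreconciled conflict between a stated severity rule and the definition of a safety endpoint. Followed literally, Protocol 8.3.5 can remove from the Grade ≥3 tables an AE that the endpoint would count. The different meaning of severe in the two documents adds a further ambiguity to the severity tables.

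The size cannot be estimated. It depends on the share of AEs at CTCAE Grade 3 or higher that do not prevent normal activities, which the documents do not give; any figure would only multiply assumptions.

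The conclusion assumes that CTCAE assigns Grade 3 or higher to some events on grounds other than preventing normal activities, and that at least some sites would follow 8.3.5 as written. It does not touch the efficacy analyses. It should be corrected, because the endpoint is named in both documents and the remedy is mainly wording.

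**What to change.** 1. In Protocol 8.3.5 and 8.3.8, record a CTCAE grade from one named version for every AE, independently of the mild, moderate or severe category. Keep the activity definitions only for events with no CTCAE term.
2. In SAP 7.2.5, state that Grade ≥3 in items i.4, vi and vii is derived from that recorded grade.
3. Give severe one meaning in both documents: either Grades 3 to 5, or Grade 3 with separate life-threatening and fatal levels.
4. Correct the SAP 7.2.2 reference to Protocol 8.3.5. The references in SAP 7.2.3 and 7.2.4 have the same numbering slip and should read 8.3.4 and 8.3.7.

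The cost is wording in the protocol, SAP and CRF guideline, plus slightly more grading work at sites, which already need CTCAE for severe events. The reported Grade ≥3 rate may rise.

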# 8.3.6 Expectedness of Adverse Event or Suspected Adverse Drug Reaction (Reference Safety Information)

An AE or suspected ADR (ie, potentially drug related AE) is considered "unexpected" if the nature, seriousness, severity or outcome of the reaction(s) is not consistent with the reference information, which is the C19-IG 20% Investigator's Brochure. The expectedness shall be determined by the sponsor for any serious ADRs (potentially related SAEs) according to the reference document for expedited safety reporting purposes.

# 8.3.7 Seriousness of Adverse Event or Suspected Adverse Drug Reaction

An AE or suspected ADR (ie, potentially drug related AE) is considered "serious" if, in the view of either the investigator or sponsor, it results in any of the following outcomes:

Death

- Life-threatening AE (life-threatening in the definition of "serious" refers to an event in which the subject was at risk of death at the time of the event; it does not refer to an event which hypothetically might have caused death if it were more severe)
- In-patient hospitalization or prolongation of existing hospitalization\*
- A persistent or significant incapacity or substantial disruption of the ability to conduct normal life functions
- A congenital anomaly/birth defect
- An important medical event (important medical event in the definition of "serious" refers
  to those events which may not be immediately life-threatening, or result in death, or
  hospitalization, but from medical and scientific judgment may jeopardize the subject
  or/and may require medical or surgical intervention to prevent one of the other outcomes
  listed above).
  - \*Hospitalization is to be considered only hospital admission (including emergency room stay) for equal or more than 24 hours. The following hospitalizations should not be reported as SAEs:
    - Hospitalization or prolongation of hospitalization needed for procedures required by the clinical trial protocol or as part of a routine procedure followed by the center.
    - Admissions not associated with an AE (eg, social hospitalization for the purpose of respite care, survey visits, or annual physicals).
    - Elective or pre-planned hospitalizations for a pre-existing condition that had not worsened from baseline (eg, elective or scheduled surgery arranged prior to start of the study).

This definition permits either the sponsor or the investigator to decide whether an event is "serious". If either the sponsor or the investigator believes that the event is serious, the event must be considered "serious" and evaluated by the sponsor for expedited reporting.

# 8.3.8 Adverse Event Documentation

All AEs and SAEs occurring on Day 1 through the Day 29 (±1 day)/Final Visit must be fully recorded in the subject's medical record and CRF, and SAE report form (if serious).

At the time of the Day 60 (±2 days) Phone Check any additional SAEs/non-serious AEs will also be collected and recorded.

It is the responsibility of the investigator to ensure that AEs are appropriately recorded.

AEs will be collected through directly observed events or spontaneously volunteered by the subject. Clearly related signs, symptoms and abnormal diagnostic procedures should preferably be grouped together and recorded as a single diagnosis or syndrome wherever possible.

The following variables must be recorded:

- The verbatim term (a diagnosis is preferred)
- Date/time of onset
- Date/time of resolution
- Severity (mild, moderate, severe [Grade 3 to Grade 5])
- Causality (unrelated, possibly related, definitely related)\*
- Seriousness (yes, no)
- Action taken (with regard to IP)
- Other action (to treat the event)
- Outcome and sequel (follow-up on AE)

\*Causality assessment will be made only when the AE occurs after the subject has initiated at least one infusion of the IP. An AE occurring before subject's exposure to IP will be always labeled as "unrelated".

For AEs that occur during infusions, the infusion rate in effect at the time of onset of the AE, the time of onset of the AE and the time of AE change materially in intensity and/or resolve will be captured.

In addition to the investigator's own description of the AE, each AE will be encoded according to the Medical Dictionary for Regulatory Activities (MedDRA).

For example, a laboratory test abnormality considered clinically significant, eg, causing the subject to withdraw from the study, requiring treatment or causing apparent clinical manifestations, or judged clinically significant in the context of the subject's medical history by the investigator, should be reported as an AE.

Each event must be described in detail along with start and stop dates, severity, relationship to IP, action taken and outcome. Each event must be adequately supported by documentation as it appears in the subject's medical or case file.

[figure not shown]
#### 8.3.9 Reporting of Serious Adverse Events

Any SAE (see Section 8.3.7) that occurs after informed consent on Day 1 through the Day 29 (±1 day)/Final Healthcare Provider Visit and any SAE recorded at the time of the Day 60 (±2 days) Phone Check must be fully recorded in the subject's medical record, CRF and SAE Report form. SAEs must be expeditiously reported whether or not considered attributable to the IP.

Serious adverse events will be reported using the designated SAE Report Form. When the investigator becomes aware of an SAE, she/he must submit a completed, signed and dated SAE Report Form (in English) within 24 hours to the sponsor by email/fax. The date of this SAE discovery by the site staff should be documented in the source documents (ie, medical records).

Each SAE must be followed up until resolution or stabilization. After the initial report, all relevant information for SAE follow-up, and for the outcome, must also be supplied to the sponsor in a timely manner (within 3 days from its identification or within 24 hours for relevant new information) by means of the SAE Report Form. In addition, the sponsor may request additional information and/or reports.

All SAE Report Forms must be reported to Grifols via email or fax as follows:

When required, and according to local law and regulations, SAEs must be reported to the IRB/EC and regulatory authorities. Copies of the investigator's reports must be sent to the sponsor.

